8.1 Primary

The primary objectives of the study are to describe the receipt of the Blincyto brochures, and knowledge and behaviours outlined in the Blincyto brochures among physicians, nurses and pharmacists.

8.2 Secondary

The secondary objectives of the study are:

- To describe the level of understanding of key safety messages in the Blincyto brochures, among physicians, nurses and pharmacists.
- To describe usage of the Blincyto brochures, among physicians, nurses and pharmacists.

This study will help indicate if the aRMMs are successful if a majority of HCPs participating in the survey confirm receipt of the brochures and demonstrate knowledge and behavior of key safety messages. These results will be interpreted in context of the wider study including the secondary objectives and the results of individual questions, response rate and recruitment. In addition, any available information external to the study to help understand the experience of the HCP aRMMs will be considered to determine what action, if any, should be taken.

Approved

9. Research Methods

9.1 Study Design

To meet the study objectives, three observational cross-sectional surveys of physicians, nurses and pharmacists are planned in France, Germany, Italy, Spain and the UK, after the introduction of Blincyto to the EU market.

The distribution of the surveys is planned to start 12 to 18 months after each country-specific launch to allow time for uptake of Blincyto and familiarity and use of the materials by the HCPs. The timing of this evaluation is sufficiently early in the product lifecycle to identify and rectify promptly any aspect of the educational program that might need to be modified.

9.2 Setting and Study Population

The surveys will be conducted in France, Germany, Italy, Spain and the UK. The selection of countries corresponds to the combination of expected product uptake and adequate timing of the product launch to allow for the completion of the study within the required timeframe. These countries have been selected to support the external validity of the study findings, as collectively they will encompass a wide range of healthcare systems: general practitioner-based gate-keeper function (UK, Spain and Italy), health insurance which is part of the social security system (Germany) and mixed (France).

This rationale is based on factors that may change as the study progresses (eg, planned country-specific launch schedule). Therefore, if recruitment of HCPs is slower than anticipated other countries may be added to meet the study timeline.

9.2.1 Study Period

The maximum planned period for data collection is 23 months. However, as product launch is planned in a staggered manner in Europe, this period is expected to be reduced in some countries.

As this is a one-wave cross-sectional design, data from HCPs will be collected at one point in time.

9.2.2 Selection and Number of Sites

Site selection and sampling strategy

The sampling frame will consist of haematology centres where Blincyto is prescribed or expected to be prescribed after its launch in each participating country. Potential sites for participation will be identified by Amgen country Regional Medical Liaison (RML)

Approved

staff. All centres in the list will be approached by RMLs to identify prescribers or potential prescribers willing to participate.

HCP selection and sampling strategy

The population for the HCP surveys will consist of haemato-oncologists, nurses and pharmacists working in haematology units. After at least one haemato-oncologist has been approached for participation, other haemato-oncologists, nurses and hospital pharmacists will be identified in the centre. Approached haemato-oncologists will also be requested to provide the name and contact details (email address or telephone number, after seeking their permission) of other haemato-oncologists, nurses who administer intravenous anti-cancer drugs and pharmacists who dispense intravenous anti-cancer drugs in their centre. In turn, identified nurses and pharmacists will be requested to provide the name and contact details of other nurses and pharmacists in their centre.

HCPs identified in each centre will be approached by [REDACTED] for participation in the surveys. Haemato-oncologists, nurses and pharmacists will be invited to participate until a cap is reached in each centre of 4 haemato-oncologists, 6 nurses and 4 pharmacists.

[figure not shown]
The number of eligible haemato-oncologists, nurses and pharmacists identified and contacted but not enrolled in the study, the number of non-respondents and the number eligible and willing to participate will be recorded.

An invitation letter will be sent by post or email with a link to the web-based questionnaire. Each invitation will include information on how to access the surveys online, and a unique participant code to ensure that the invitation is used only once. If the target level of HCPs is not reached after two emails or postal mailings, non-responding HCPs will be contacted by telephone.

The overall sampling strategy is depicted in [Figure 1](#).

Approved

Figure 1. Illustration of Sampling Strategy

9.2.3 Healthcare Professional Eligibility

This study is comprised of cross-sectional surveys of physicians, nurses and pharmacists, which can be considered as three strata for the analysis.

9.2.3.1 Inclusion Criteria

- Physician, nurse or pharmacist has managed, administered or prepared Blincyto for at least one adult patient with Ph- R/R B precursor ALL.

9.2.3.2 Exclusion Criteria

- Physician, nurse or pharmacist has been employed by Amgen (or delegate).
- Physician, nurse or pharmacist has participated in the pre-testing phase of the HCP survey.

9.2.4 Baseline Period

This study consists of three cross-sectional surveys that do not involve any follow-up. Eligibility criteria will be assessed and HCP questionnaires will be completed at one point in time within the data collection period.

9.3 Variables

The surveys will examine the effectiveness of the educational materials targeting physicians, nurses and pharmacists about the risks associated with Blincyto treatment and the best course of action to undertake in order to minimise these risks.

Three questionnaires will contain multiple-choice questions with no free text fields.

Approved

The questionnaire will be structured as follows:

- A. Acceptance to participate (date and signature)
- B. Screening: eligibility, demographics
- C. Main questionnaire domains

Section B (Screening) will collect socio-demographic characteristics (age group, gender and experience) about HCPs to explore factors associated with understanding and implementation of key messages. The questionnaire will be designed to take a maximum of 15 minutes to complete.

The questionnaire will assess the following key concepts related to each of the brochures:

- Receipt of the brochures.
- Knowledge and understanding of key messages.
- Behaviors outlined in the brochures including the distribution of educational brochures to patients/caregivers.
- Usage of the brochures ie, whether HCPs read and refer to the educational materials and reasons for not reading them.

9.3.1 Outcome Assessment

The primary endpoints for the HCP survey are:

- Receipt: A categorical variable will describe the proportion of physicians, nurses and pharmacists who report having received the brochure.
- Knowledge: A mean score will be created to summarise individual physician, nurse and pharmacist scores. An individual physician, nurse or pharmacist score is calculated as the proportion of all knowledge questions with correct responses.
- Behaviour: A mean score will be created to summarise individual physician, nurse and pharmacist scores. An individual physician, nurse or pharmacist score is calculated as the proportion of all behavior questions with correct responses. For physicians and nurses, the score will also include the adequacy of the timing for the distribution of the card and brochure to patients/caregivers. Among physicians and nurses who do not distribute the materials to patients/caregivers, a categorical variable will describe the reasons for non-compliance.

The secondary endpoints for the HCP survey are:

- Understanding: Among physicians, nurses and pharmacists who have read the educational materials, an ordinal scale will assess the self-reported level of understanding.
- Usage: A categorical variable will describe the proportion of physicians, nurses and pharmacists who report having read the brochure. Among those physicians, nurses and pharmacists who have read the educational material, an ordinal scale will assess how often the material was referred to. Among those who do not read the materials, a categorical variable will describe the reasons for not reading them.

Approved

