ADR	Adverse Drug Reaction
ALL	Acute Lymphoblastic Leukaemia
aRMM	additional Risk Minimisation Measure
CIOMS	Council for International Organizations of Medical Sciences
eDC	Electronic Data Capture
EMA	European Medicines Agency
EU	European Union
GVP	Good Pharmacovigilance Practice
HCP	Healthcare Professional
HSCT	Stem cell transplantation
MAH	Marketing Authorisation Holder
ME	Medication Error
MedDRA	Medical Dictionary for Regulatory Activities
OS	Overall Survival
PASS	Post-Authorisation safety Study
Ph-	Philadelphia chromosome–negative
RML	Regional Medical Liaison
RMP	Risk Management Plan
R/R	Relapsed/Refractory

Approved

3. Responsible Parties

MAH	Amgen is the MAH which oversees MAH activities and facilitates Competent Authority submissions [REDACTED] [REDACTED] [REDACTED] [REDACTED] [REDACTED]
MAH Representative	The MAH representative for this study is [REDACTED], a Clinical Research Organisation (CRO) delegated to serve as the study coordinating centre. [REDACTED] will conduct the study on behalf of Amgen. The MAH representative is responsible for overall conduct, deliverables and timelines for the study and communication with Amgen. [REDACTED] [REDACTED] [REDACTED] [REDACTED]

4. Abstract

- **Study Title:**

Survey of physicians, pharmacists, and nurses involved in the prescribing, preparation and administration of Blincyto in Europe to evaluate the effectiveness of additional risk minimization measures.

- **Study Background and Rationale:**

Blincyto[®] (blinatumomab) is indicated for the treatment of adults with Philadelphia chromosome–negative (Ph-) relapsed or refractory (R/R) B-precursor acute lymphoblastic leukaemia (ALL) as a continuous infusion. Due to the seriousness and rarity of the indication, and the lack of alternative medicinal products for the subset of patients with Ph- disease, Blincyto was designated by the European Medicines Agency (EMA) as an orphan medicinal product. The product was approved in November 2015 and is due to become available throughout the EU according to country-specific timelines.

During the marketing authorisation application, two important safety risks were identified to require additional risk minimisation measures (aRMMs): neurological events and the potential for medication errors (MEs).

A condition to the marketing authorisation for the safe and effective use of Blincyto is the implementation of aRMMs consisting of educational materials targeting healthcare

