professionals (HCPs; physicians, pharmacists, nurses), as well as patients/caregivers. Educational materials for HCPs include brochures for physicians, nurses and pharmacists.

In line with regulatory guidance (eg, EMA GVP XVI and GVP VIII) a survey of physicians, nurses and pharmacists is herein presented to help assess whether the processes put in place for the Blincyto educational efforts are effective in achieving a sufficient level of receipt of the materials, and knowledge and behaviour around key messages in the materials. A survey of patients/caregivers is also proposed but described in a separate protocol.

- **Research Question and Objective(s)**

- Primary Objectives

The primary objectives of the study are to describe the receipt of the Blincyto brochures, and knowledge and behaviours outlined in the Blincyto brochures among physicians, nurses and pharmacists.

- Secondary Objectives

- To describe the level of understanding of key safety messages in the Blincyto brochures, among physicians, nurses and pharmacists
- To describe usage of the Blincyto brochures, among physicians, nurses and pharmacists.

- Hypothesis(es)/Estimation

This study is descriptive and therefore no formal hypothesis will be tested.

This study will help indicate if the aRMMs are successful if a majority of HCPs participating in the survey confirm receipt of the brochures and demonstrate knowledge and behavior of key safety messages. These results will be interpreted in context of the wider study including the secondary objectives and the results of individual questions, response rate and recruitment. In addition, any available information external to the study to help understand the experience of the HCP aRMMs will be considered to determine what action, if any, should be taken.

- **Study Design/Type**

This is an observational study consisting of three cross-sectional surveys of physicians, nurses and pharmacists to help evaluate the effectiveness of the educational brochures in minimising the risk of MEs and neurological events. The distribution of the three HCP surveys is planned to start 12 to 18 months after each country-specific launch to allow time for uptake of Blincyto and familiarity and use of the materials by the HCPs.

Approved

- **Study Population or Data Resource**

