Patients initially receive 2 cycles of treatment. Based on an individual benefit-risk assessment, 3 additional cycles of Blincyto consolidation treatment may be considered if complete remission has been achieved. A single cycle of treatment is 4 weeks of continuous infusion and each cycle of treatment is separated by a 2 week treatment-free interval.

Blincyto safety profile

During the marketing authorisation application, two important safety risks were identified to require additional risk minimisation measures (aRMMs): neurological events and the potential for medication errors (MEs).

Neurological events such as fits, problems with speech, alterations in consciousness, confusion and disorientation, problems with balance and coordination occur in approximately 50% of patients treated with Blincyto ([Topp et al. 2015](#)).

Blincyto is infused continuously using a pump device. Hospitalisation is recommended for initiation at a minimum for the first 9 days of the first cycle and the first 2 days of the second cycle. Blincyto may be administered at home after discharge with an ambulatory pump. Medication errors can occur at any time during the reconstitution, dilution and administration of Blincyto that may result in patients receiving a dose that is too high or too low. Mistakes in setting up the pump, or problems with the pump can also cause MEs. In the pivotal phase II trial that led to the approval of Blincyto in the EU, MEs were observed in 3.2% (6/189) of subjects ([Topp et al. 2015](#)). In the pooled safety dataset, which includes [REDACTED] patients exposed to Blincyto in [REDACTED] studies of different indications (not including the phase III trial), MEs were reported in [REDACTED] of subjects. [REDACTED]

[REDACTED] Overdoses were primarily due to infusion pump errors and Blincyto preparation errors. Most MEs did not result in an adverse

Approved

event. Of the ones associated with adverse events, most events were consistent with the known safety profile, mild in severity, and resolved.

Blincyto additional risk minimisation

As a requirement linked to the Blincyto Risk Management Plan (RMP), Amgen as the Marketing Authorisation Holder (MAH), shall ensure that in each member state where Blincyto is marketed all healthcare professionals (HCPs) who are expected to prescribe, dispense or administer the product, and patients/caregivers who are expected to use the product, be provided with the aRMMs presented in [Table 1](#).

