9.5 Study Size

Based on precision calculations provided in [Table 2](#) and [Table 3](#), sample sizes for each survey are planned as follows:

- Physician and pharmacist surveys: the study aims to include approximately [REDACTED] physicians and [REDACTED] pharmacists to allow precisions of [REDACTED] for correct responses of 60% and 90%, respectively, for the primary endpoint question of receipt. For the score of correct responses to knowledge and behavior questions ranging from 0 to 10, a sample size of [REDACTED] would produce two-sided 95% confidence intervals with a distance from the mean to the confidence limits ranging from [REDACTED] when the estimated standard deviation ranges from [REDACTED], respectively.
- Nurse survey: the study aims to include up to [REDACTED] nurses to allow precision of [REDACTED] for correct responses of 60% and 90%, respectively, for the primary endpoint question of receipt. For the score of correct responses to knowledge and behavior questions ranging from 0 to 10, a sample size of [REDACTED] would produce a two-sided 95% confidence interval with a distance from the mean to the limits ranging from [REDACTED] when the estimated standard deviation ranges from [REDACTED] respectively.

The approach to the study sample size for the HCP surveys is governed chiefly by the assumed percentage of HCPs who correctly respond to the questions, the acceptable precision around this assumed estimate and the degree of intra-class correlation. For practical reasons, we will aim to recruit more nurses than doctors and pharmacists as more nurses are expected to have contact with patients and are more likely to participate.

Approved

Table 2. Precision of Survey for [REDACTED] Nurses and [REDACTED] Physicians and Pharmacists According to a Range of Correct Response Rates to the Primary Endpoint Question of Receipt Using the Clopper-Pearson Method

Sample size	Correct Response	Lower Limit	Upper Limit
[REDACTED]	60%	[REDACTED]	[REDACTED]
[REDACTED]	70%	[REDACTED]	[REDACTED]
[REDACTED]	80%	[REDACTED]	[REDACTED]
[REDACTED]	90%	[REDACTED]	[REDACTED]
[REDACTED]	60%	[REDACTED]	[REDACTED]
[REDACTED]	70%	[REDACTED]	[REDACTED]
[REDACTED]	80%	[REDACTED]	[REDACTED]
[REDACTED]	90%	[REDACTED]	[REDACTED]
[REDACTED]	60%	[REDACTED]	[REDACTED]
[REDACTED]	70%	[REDACTED]	[REDACTED]
[REDACTED]	80%	[REDACTED]	[REDACTED]
[REDACTED]	90%	[REDACTED]	[REDACTED]
[REDACTED]	60%	[REDACTED]	[REDACTED]
[REDACTED]	70%	[REDACTED]	[REDACTED]

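### For physicians and nurses, the pooled knowledge and behaviour scores cannot show whether the brochures work for each of the two target risks

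*Protocol*

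**What the plan says.** The Abstract (Section 4) states that "two important safety risks were identified to require additional risk minimisation measures"; it and Section 7.1 name them as neurological events and medication errors. Under Study Design/Type, the Abstract gives the purpose of the surveys as helping to evaluate "the effectiveness of the educational brochures in minimising the risk of MEs and neurological events".

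Section 9.3.1 defines the primary knowledge endpoint as the mean of individual scores, where "An individual physician, nurse or pharmacist score is calculated as the proportion of all knowledge questions with correct responses". For behaviour, the individual "score is calculated as the proportion of all behavior questions with correct responses". In the physician and nurse surveys, this behaviour score additionally counts whether the patient card and brochure were handed out at a suitable time. The Abstract and Section 9.7.2.4 repeat these rules. None of the three places has a weight, domain, minimum or sub-score by risk.

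The subgroups in 9.7.2.5.1 are respondent features: country, whether the brochure was read, recency of contact with a treated patient, and trial participation. Section 8.2 sets out how the results will be read. It looks for a majority of respondents showing knowledge and behaviour, gives no score threshold, and includes individual-question results among the context for interpretation.

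In Appendix F the physician and nurse brochures each cover both risks. The pharmacist brochure covers reconstitution and preparation only.

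**The concern.** Section 9.1 justifies the survey's timing by the wish to find and correct weak parts of the educational programme early. That needs a result that says which part is weak. A single proportion over all items does not. The same mean can come from moderate knowledge of both risks, or from good knowledge of one and poor knowledge of the other. The risk with more items carries more of the score, and the Protocol does not say how items are divided between the risks.

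For physicians and nurses the behaviour score also takes in a third element, the timing of handing out the patient card and brochure, which belongs to neither risk. At stake is whether the headline result can support a statement about each of the two risks that the materials were written to reduce.

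**Working it through.** **Inputs**

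- Scoring rule: one proportion of all items correct, for knowledge and for behaviour (9.3.1). Section 9.5 speaks of a score "For the score of correct responses to knowledge and behavior questions ranging from 0 to 10", with the leading words applying to both domains. I take the 0-10 score as ten times the proportion.
- Item mix: not in the Protocol, because Appendix A lists the questionnaires as stand-alone documents. The neurological share w is therefore an assumption and is shown as a range.
- Table 1: of four nurse messages, two are neurological (monitoring and management; driving and whom to contact). This gives w = 0.50.
- Nurse brochure (Appendix F): about 12 administration points (IV lines 2, pump 6, bag change 1, interruption 1, catheter 2), or up to 15 if compound points are split. There are 4 neurological points, or 6 if the two pieces of advice to patients are counted separately. Bullet breaks are partly lost in the extracted text, so these counts are approximate.

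**Step 1. The plan's own precision figures.** Table 3 gives half-widths for the 0-10 score. Its caption names Clopper-Pearson, but the visible figures match a t interval for a mean, t(0.975, n−1) × SD / √n. Row sizes are redacted; n = 110, 105 and 100, inferred from the 90-110 nurse range in the caption, reproduce all 12 visible cells. Examples:

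- n = 110, SD 3.5: 0.661, shown as 0.66 (a normal quantile would give 0.654).
- n = 100, SD 2.5: 0.496, shown as 0.50.
- n = 100, SD 3.5: 0.694, shown as 0.69.

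**Step 2. Score of a nurse with no neurological item right.** With all other items right, the score is 10 × (1 − w).

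| Assumed item mix | w | Score |
|---|---|---|
| Table 1, 2 of 4 messages | 0.50 | 5.0 |
| Brochure, 12 administration : 6 neurological | 6/18 = 0.33 | 6.7 |
| Brochure, 15 : 6 | 6/21 = 0.29 | 7.1 |
| Brochure, 12 : 4 | 4/16 = 0.25 | 7.5 |
| Brochure, 15 : 4 | 4/19 = 0.21 | 7.9 |

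**Step 3. Sensitivity.** The questions are multiple choice (9.3), so guessing adds to the score. With an assumed one-in-four chance on the neurological items, the score is 10 × [(1 − w) + 0.25w]: 6.3 at w = 0.50, 7.5 at 0.33 and 8.1 at 0.25. If instead only 90% of the other items are right and there is no guessing, it is 10 × 0.9 × (1 − w): 4.5 at w = 0.50, 6.3 at 0.30 and 7.2 at 0.20.

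**Step 4. Two profiles, one score.** At w = 0.30, a nurse with all other items right and no neurological item right scores 10 × 0.70 = 7.0. A nurse with 70% right on both kinds of item also scores 7.0. The pooled score cannot tell them apart.

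**Step 5. Precision of sub-scores.** A sub-score rescaled to 0-10 uses the same respondents, so at a given SD its half-width is the one for the total. With 100 nurses this is 0.50 at SD 2.5 and 0.69 at SD 3.5. With 40 to 60 physicians it is 0.80 to 0.65 at SD 2.5 and 1.12 to 0.90 at SD 3.5. Fewer items will probably raise the SD, moving a sub-score towards the wider figures. Like Table 3, the formula treats respondents as independent.

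**The case against.** The strongest reply is that the Protocol already looks below the total. Section 8.2 interprets the scores in the context of individual questions, and 9.7.2.1 provides counts, percentages and, as appropriate, 95% intervals for categorical data. Widespread failure on neurological items would then show up question by question, and item results may be the better guide to which text to revise. The study is descriptive, no decision is triggered by the total alone, and table layout is left to the SAP (9.7), which may add domain summaries.

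Much of this stands. The gap would not be invisible, and that keeps the point minor. What remains is that the primary score is fixed in the Protocol itself, that 9.7.2.4 lists no item-level or per-risk analysis, and that separate item percentages are not a prespecified estimate with an interval for each risk.

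It is also fair that tagging is not clean, since items on hospitalisation or interruption may bear on both risks, and that a 15-minute questionnaire may leave few items per risk.

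Two stronger readings are tempting, and the documents support neither:

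- A reader might set a score of 7.5 against the 60% to 90% range in 9.5 and call it a good result. That range concerns receipt of the brochure. For the scores, 9.5 assumes only standard deviations.
- A reader might argue that the score hides failure on the more frequent risk, since neurological events occur in about half of patients while "MEs were observed in 3.2% (6/189) of subjects". This sets the frequency of an adverse reaction against that of an error in one trial, and the pooled medication-error figure is redacted. Neither figure says which message is more likely to fail to get through.

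**Conclusion.** The point holds for physicians and nurses at low severity. Each primary score pools all items, so the primary result does not show whether the materials work for each risk. It does not extend to pharmacists, whose brochure deals with preparation only.

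The size is conditional on the unseen item mix: 5.0 of 10 under the Table 1 split, about 6.7 to 7.9 under the nurse-brochure split, for a nurse with no neurological item right and every other item right. Because no cut-off for a good score is set, it cannot be said that such a nurse passes or scores well.

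These figures are for nurses' knowledge. I computed none for behaviour or for physicians, and the nurse ratio should not be carried over: the physician brochure gives much of its text to neurological events, so pooling there could equally hide weak knowledge of medication errors. What carries over is the pooling rule. Planned use of individual-question results limits the harm but does not replace a prespecified summary per risk.

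**What to change.** Before data collection, tag each knowledge and behaviour item in the physician and nurse questionnaires as medication error, neurological event or other. Put distribution timing and items that fit both risks under other.

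In 9.7.2.4, add for physicians and nurses a knowledge and a behaviour sub-score per risk, each with a 95% interval, beside the pooled total, wherever a risk has enough items. State that minimum number of items in advance. Require the conclusion to cite the sub-scores as well as the total. The pooled primary endpoint and the pharmacist analysis can stay as they are.

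The cost is the tagging and a few table rows, with no extra respondents or questions. The downside is that sub-scores rest on fewer items and are likely to be less precise than the total; for some domains a risk may have too few items to report.
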